**PROTOCOL TITLE: Oxytocin to Enhance Alcohol Behavioral Couple Therapy**

**PRINCIPAL INVESTIGATOR: [name].**

**ClinicalTrials.gov ID: Pro00082233**

**Document Date: March 8, 2022**

## 1.0 Objectives / Specific Aims

Identifying effective medications to treat alcohol use disorder (AUD) is a national public health priority. Combining pharmacological interventions with evidence-based behavioral treatments may help maximize and sustain AUD treatment outcomes. Alcohol Behavioral Couples Therapy (ABCT) is a manualized, evidence-based psychotherapy for the treatment of AUD that simultaneously targets relationship functioning, which is an important mechanism in the etiology, course, and treatment of AUD. While adaptive relationship functioning facilitates successful treatment engagement and outcomes, maladaptive relationship functioning interferes with AUD recovery and is a precipitant of relapse. Thus, ABCT employs cognitive behavioral techniques to (1) reduce alcohol consumption, (2) enhance partners' skills to facilitate recovery (e.g., communication, managing cravings together), and (3) enhance relationship functioning. Although ABCT is a highly efficacious treatment, there is room for improvement in outcomes, as more than half of ABCT patients report hazardous drinking episodes during treatment and a similar proportion fail to achieve abstinence.

The neuropeptide oxytocin is a promising candidate to enhance ABCT via neurobiological and behavioral pathways including its potential to restore sensitivity to natural rewards such as interpersonal relationships. Neuroimaging studies indicate that dysregulation of corticolimbic brain circuitry is centrally involved in AUD pathophysiology. Individuals with AUD demonstrate lower corticolimbic connectivity than healthy controls and disrupted corticolimbic connectivity is associated with AUD relapse. Notably, oxytocin increases corticolimbic connectivity. Behaviorally, human and animal studies indicate that oxytocin reduces alcohol withdrawal, tolerance, craving and self-administration. However, emerging literature emphasizes individual differences such as sex, social context, and psychosocial history that moderate the effects of oxytocin on social behavior. Pilot data from our team revealed that among distressed couples with substance use disorders, oxytocin was associated with worse conflict behaviors among female partners, but did not affect male partners' behavior. These nuanced findings may be explained by the social salience hypothesis, which proposes that rather than selectively enhancing prosocial behavior, oxytocin might universally amplify an individual's current social tendencies which, in the context of addiction and relationship distress and without corrective intervention, may be maladaptive. ABCT has demonstrated the ability to insulate couples from maladaptive relationship behaviors that are proven antecedents to hazardous drinking and relapse by cultivating and implementing new adaptive skills that facilitate recovery. Notably, treatment gains are greater among couples who begin ABCT with poorer relationship functioning and greater psychiatric comorbidity and within-session gains predict positive ABCT outcomes. Thus, a key approach to the therapeutic translation of oxytocin is to combine oxytocin with a behavioral intervention such as ABCT to reduce alcohol consumption. Doing so will ensure that oxytocin has an adaptive platform to enhance the positive gains made within ABCT sessions.

The proposed study will test the efficacy of oxytocin to enhance ABCT outcomes. We will also determine the effects of treatment on corticolimbic connectivity using blood oxygen level dependent (BOLD) functional magnetic resonance imaging (fMRI). In order to accomplish this, we will employ a double-blind, placebo-controlled, randomized study design and examine standardized, repeated, dependent measures of change in: (1) alcohol consumption, (2) relationship functioning, and (3) corticolimbic connectivity in response to a validated in-scanner cue paradigm. Couples (N=100) will be randomly assigned to receive oxytocin (40 IU) or placebo prior to each of 12 weekly ABCT therapy sessions. The following specific aims are proposed:

**Specific Aim 1:** Compare the efficacy of ABCT with oxytocin vs. placebo in reducing alcohol consumption.

**Specific Aim 2:** Compare the efficacy of ABCT with oxytocin vs. placebo in improving relationship functioning.

**Specific Aim 3:** Use neuroimaging to determine the effects of treatment on corticolimbic connectivity in response to alcohol and relationship conflict cues.

## 2.0 Intervention to be studied

**Study Medication, Dosage, and Administration.** A 40-IU dose of oxytocin or matching placebo will be self-administered 30 minutes prior to the start of each weekly ABCT session. The dose and timing of medication administration is based on past research in our group and others, and determined in consultation with NIAAA program staff. Study prescribers ([name], P.A. and [name].) will conduct the H&P exams, provide prescriptions for oxytocin, and assist with weekly assessment of adverse events. Investigational Drug Services (IDS) at MUSC or Pitt Street Pharmacy in Mt. Pleasant will compound and dispense oxytocin and matching placebo. Research staff will instruct participants on the correct method of administration to achieve the desired dose and will observe participants' self-administration. Participants will blow their nose, exhale through their nose, then spray into one nostril while inhaling, alternating nostrils until the 40 IU dose is achieved. A 40 IU dose has demonstrated extensive safety and efficacy, is within the normal dosing range, and one of the most common concentrations utilized in human research. Randomization will be carried out by a research pharmacist not involved in clinical management of participants in order to preserve the double-blind design.

**Psychosocial Intervention: Alcohol Behavioral Couple Therapy (ABCT).** All participants will receive 12 weekly, 90-minute ABCT therapy sessions delivered by trained Masters or Doctoral-level clinicians consistent with the published manual. The main goal of ABCT is to concurrently reduce AUD symptom severity and improve relationship functioning. Patients receive psychoeducation pertaining to the interconnectedness of AUD and relationship functioning. AUD-focused components of the treatment help patients identify and manage cravings, urges to drink, and thoughts about alcohol use; enhance individual problem solving and decision-making abilities; identify and plan for "high-risk" situations in which vulnerability to relapse is heightened; learn drink refusal skills; and cope with a potential relapse. ABCT also teaches couples to work together to enhance reciprocity and communication skills in the relationship, increase positive rewards of initiating and maintaining drinking reductions and abstinence, and identifying and implementing ways partners can help minimize and manage alcohol use triggers, participate in drink refusal skills, and help prevent relapse.

## 3.0 Study Endpoints

**Primary Outcome Measures.** Primary outcomes include (1) alcohol consumption (percent days abstinent and heavy drinking as measured by the TLFB) and (2) relationship functioning (DAS-7). Additional AUD outcomes include alcohol craving (PACS) and ethanol metabolites and traditional biomarkers (e.g., EtG and PEth) to corroborate participant self-reports of abstinence and alcohol use. PEth is among the most specific biomarkers used to detect heavy drinking and monitor abstinence. The conjugated alcohol metabolite EtG remains positive in urine for several days following cessation and is a useful biomarker of recent drinking in outpatient settings. Selected assessment instruments are standardized, have good psychometric properties, are widely used, and have been used extensively by our research group.

### *AUD Symptom Severity*

- **Time Line Follow-[name] (TLFB):** The TLFB, which uses a calendar to stimulate recall, will assess consumption of alcohol (e.g., number of standard drink units, percent of days drinking and abstinence, time span in which drinks were consumed), drugs, and tobacco for 60 days prior to study entry, and during the treatment and follow-up phase.

### ***Relationship Functioning***

- **Dyadic Adjustment Scale-7 (DAS-7):** The self-report DAS-7 is based on the original 32-item measure. It is used to assess domains relationship functioning and has demonstrated strong psychometric properties.

## **4.0 Inclusion and Exclusion Criteria/ Study Population**

All participants will be at least 18 years of age. Women and members of minority groups will be eligible for participation.

Inclusion criteria are: 1) aged 18- 75, 2) English fluency and intellectual functioning sufficient to provide informed consent and accurately complete assessments and participate in treatment (as assessed by a criterion of  $\leq 26$  on the Mini-Mental Status Exam [MMSE]), , 4) married, cohabiting, or in a committed relationship for  $\geq 6$  months, 5) one partner must meet DSM-5 diagnostic criteria for current (i.e., past 12 months) alcohol use disorder (assessed via the Quick Structured Clinical Interview for DSM-5 Disorder). Couples in which both partners meet diagnostic criteria for current AUD are eligible for participation, 6) maintenance of psychotropic medications on a stable dose for at least 4 weeks before study initiation, and 5) concurrent substance use disorders (e.g., marijuana) are acceptable provided that alcohol is the participant's primary substance of choice. The inclusion of participants with substance use disorders is essential because of the marked frequency of co-occurrence among patients with AUD.

Exclusion criteria include: 1) meeting DSM-5 criteria for a history of or current psychotic or bipolar affective disorders, 2) current suicidal or homicidal ideation and intent, 3) a history of seizures and/or a seizure disorder per the judgement of the medical clinician, 4) severe, unilateral intimate partner violence in the past 6 months as defined by the Revised Conflict Tactics Scale, and 5) pregnancy or breastfeeding for women, 6) Acute alcohol withdrawal as indicated by CIWA-Ar scores  $>8$ , Attendance at therapeutic activities other than study sessions will be closely monitored using the Treatment Services Review, 7) any unstable or serious medical condition affecting the potential participant's ability to participate in the study, 8) Individuals with claustrophobia; tattoos above the shoulders; permanent eyeliner or permanent artificial eyebrows; cardiac pacemaker; metal fragments in eye, skin, or body, including shrapnel; heart valve replacement; brain clips; venous umbrella; current or former sheet-metal worker or welder; lifetime history of aneurysm surgery; lifetime history of seizures and/or epilepsy per the judgement of the medical clinician; intracranial bypass, renal, or aortic clips; prosthetic devices such as middle ear, eye, joint, or penile implants; joint replacements; non-removable hearing aid, neurostimulator, or insulin pump; shunts/stents; metal mesh/coil implants; metal plate/pin/screws/wires; or any other MRI contraindications as determined by the MRI technician at the time of scanning will not be eligible to participate in the neuroimaging component of the study, however individuals who meet inclusion/exclusion criteria for the medication component of the study but not the MRI portion will still be eligible to reenroll in and complete the medication/treatment phase.

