Female participants who complete appointments via telehealth will be required to take an at-home urine pregnancy test during those visits (provided by study team) and confirm a negative result (verbally and with photo of dipstick). The pregnancy tests used in this study are designed for at-home use, come with clear and simple instructions. In very rare and highly unlikely circumstances where the participant is unfamiliar with how to provide a urine sample or take an at-home pregnancy test, study staff can provide further instructions on how to provide a urine sample, how use the dipstick to test, and to differentiate between a positive and negative result. Ability and willingness to perform an at-home pregnancy test is required for telehealth female participants.

Study medication and other study required study materials will be shipped overnight from research pharmacy to participant's designated location at the agreed upon date using overnight shipping with contracted shipping company (FedEx, UPS) and with appropriate ice packs and temperature monitoring device as well as a signature requirement at delivery. Regarding all telehealth participants (including out of

state): Research participants will be asked to retrieve the study drug from their refrigerator at the beginning of each check-in video telehealth session with study staff. Participants will self-administer the medication while in view of the study staff on screen. Once medication is administered, participant will be instructed to return drug to their refrigerator prior to continuing with the remainder of the appointment.

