#### *Exclusion criteria*

- 1) Meeting DSM-5 criteria for a history of or current psychotic or bipolar affective disorders, or with current suicidal or homicidal ideation and intent. Those individuals will be referred clinically for treatment.
- 2) Participants who present a serious suicide risk or are likely to require hospitalization during the study.
- 3) Participants on psychotropic medications which have been initiated during the past 4 weeks. They may be re-assessed after at least four weeks on a stable dose.

- 4) Acute alcohol withdrawal as indicated by CIWA-Ar scores >8. They may be re-assessed once they are no longer in withdrawal. Those individuals will be referred for medically supervised detoxification.
- 5) Severe unilateral intimate partner violence in the past 6 months as defined by the CTS-2.
- 6) Pregnancy or breastfeeding for women.
- 7) Individuals with implanted metal devices above the waist will be eligible to enroll in the clinical trial but will not be eligible to participate in the neuroimaging component of the study.

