Study Safety. [name] (PI) or [name] (Co-I) will be present or on call at the time of all study visits. The proposed study does not involve alcohol or drug administration. Females who are pregnant or breastfeeding are ineligible to participate due to the known effects of the study drug (oxytocin) on parturition and lactation. Couples must agree to use a reliable method of birth control and female participants will complete pregnancy tests each week during the treatment phase (for telehealth participants, pregnancy tests will be provided and study staff will require a verbal confirmation of negative pregnancy test prior to medication administration). If one of the participants becomes pregnant during the trial (despite the requirement to use an approved method of contraception), the study staff will continue to follow the participant through the course of the pregnancy. Further, since this is an intent-to-treat trial, participants will be allowed to continue to engage in therapy offered as part of standard of care in this trial. Participants who become pregnant will no longer be allowed to engage in the experimental portion of the trial and the study medication will no longer be administered. Additionally, they will not be asked questions or administered surveys regarding illegal substance use. Participants who become pregnant will also be excluded from completing urine drug screens. Since ABCT is the standard of care for couples where one individual meets AUD criteria, continuing to allow both participants to participate in the standard of care portion of the trial holds the prospect of direct benefit to the participant and is in the best interest of the participant. Protocols for reported AEs and SAEs are outlined above. All unexpected AEs and SAEs will be monitored until resolved. A detailed summary of all AEs will be prepared weekly by the research staff. At the weekly team meetings (or before if urgent), the research staff will report any premonitory symptoms of clinical deterioration. Study procedures will follow the FDA's Good Clinical Practice Guidelines ([www.fda.gov/oc/gcp](http://www.fda.gov/oc/gcp)). Any outside requests for information or any breaches in confidentiality will be reported to [name]. All requests by participant's physicians and other medical providers will be referred directly to the applicant.

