## **14.0 Risks to Subjects**

Oxytocin Safety: Oxytocin is a neuropeptide commonly administered intravenously among women during childbirth. Risks associated with oxytocin administration have been noted among women given intravenous, but not intranasal, oxytocin for its FDA-approved purpose to induce labor and facilitate lactation. These risks include seizures, mental disturbances, nausea, vomiting, irregular heartbeat, high blood pressure, and unexpected bleeding or contraction of the uterus and have been observed in a small number of women. However, preliminary studies conducted by our group and others indicate that risks of intranasal oxytocin administration at the planned dose of 40 IU is minimal and manageable through the proposed human participants protection methods. Our group has administered intranasal oxytocin at this dose to over 300 research participants to date, including distressed couples with AUD and intimate partner violence, without a single adverse event reported. Participants will be informed about the potential side effects of oxytocin and will be closely monitored by the research team. Oxytocin self-administration will occur only in the context of the study visit with clear instruction from the study staff, who are equipped with ready access to clinicians and emergency care if necessary. All participants will be given clear instructions on when and where to administer the study medication (only during the study visit, while study staff are monitoring). The study medication will be stored in under refrigeration before and after medication administration (either at the participant's home or at the study site).

All telehealth participants complete a participant locator form with study staff, that allows the study team to identify local emergency care facilities and contact information. Specifically, for out of state or remote participants, the study staff will compile a list of referrals and emergency contacts to provide to study participants ahead of enrollment.

Blood Draw: Participants may experience pain or discomfort, faintness, bruising, or bleeding at the location where the blood is drawn. There is also a slight chance of infection as a result of having blood drawn.

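### The protocol carries two eligibility lists that do not match and two versions of the telehealth pregnancy check, and nothing says which governs

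*Combined protocol and SAP*

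**What the plan says.** Eligibility is set out twice, in Section 4.0 and again under Inclusion/Exclusion Criteria in Section 12.0.

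- **Seizures and medical conditions.** Section 4.0, exclusion 3, is "a history of seizures and/or a seizure disorder per the judgement of the medical clinician". Exclusion 7 covers unstable or serious medical conditions that affect ability to take part. The Section 12.0 exclusion list, numbered 1 to 7, has no counterpart to either.
- **Metal and the optional scan.** Section 4.0, exclusion 8, bars from scanning people with metal fragments in the body, joint replacements, or plates, pins, screws or wires, without limiting this to a body region. It adds any other contraindication that the MRI technician finds. Section 12.0, exclusion 7, says: "Individuals with implanted metal devices above the waist will be eligible to enroll in the clinical trial", but not to be scanned. It names no other metal.
- **Telehealth pregnancy check.** General Procedures in Section 9.0 and the first Telehealth statement on the subject ask for verbal confirmation. Study Safety in Section 12.0 says: "study staff will require a verbal confirmation of negative pregnancy test prior to medication administration". A later Telehealth paragraph in Section 9.0 requires women to "confirm a negative result (verbally and with photo of dipstick").

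**The concern.** A protocol that states eligibility twice needs the two statements to agree, or needs a sentence saying which prevails. This one has neither. The Section 12.0 list reads as a complete list rather than a pointer. It is numbered, it restates Section 4.0 items such as "Severe unilateral intimate partner violence in the past 6 months as defined by the CTS-2", it adds wording of its own (for example, people likely to need hospitalization during the study), and it does not refer back to Section 4.0.

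The lists are also used. Section 14.0 says that the screening measure asks about the inclusion and exclusion criteria, and one withdrawal rule in its Safety and Monitoring Plan depends on them. A screening form built from Section 12.0 would not ask about seizures or unstable medical conditions. A telehealth visit run from the shorter pregnancy statements would not collect a photograph. The telehealth check matters because no biological specimens are collected from these participants, so the home test is the only pregnancy test before dosing. The protocol itself gives oxytocin's known effects on parturition and lactation as the reason for excluding pregnant and breastfeeding women.

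**Working it through.** No arithmetic applies. The check is an item-by-item comparison of current text.

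| Point | One place | Another place | Result |
|---|---|---|---|
| Seizure history | Section 4.0, exclusion 3: excluded, on the medical clinician's judgement | Section 12.0, exclusions 1 to 7: no entry | Present in one list, absent from the other |
| Unstable or serious medical condition | Section 4.0, exclusion 7: excluded | Section 12.0, exclusions 1 to 7: no entry | Present in one list, absent from the other |
| Metal (scan only) | Section 4.0, exclusion 8: fragments, joint replacements and fixation hardware, no body-region limit | Section 12.0, exclusion 7: implanted devices above the waist | Different scope |
| Telehealth pregnancy check | General Procedures; first Telehealth statement; Study Safety: verbal | Later Telehealth paragraph: verbal plus photograph | Three statements against one |
| MMSE (inclusion) | Section 4.0: 26 or below | Section 12.0: above 26 | Directly opposed |

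**Seizures and medical conditions.** Section 12.0 does not say that such people may enter; it is silent. The conflict is therefore an omission from a list that presents itself as complete.

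**Metal.** Take a joint replacement or a screw below the waist. The Section 4.0 list excludes it from scanning, and the Section 12.0 list does not mention it. The written criteria therefore give different answers for the same person.

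**Pregnancy check.** Of the three verbal statements, two (the first Telehealth statement and Study Safety) are tied to giving study medication. The photograph is tied to telehealth visits rather than expressly to dosing. Telehealth participants take the drug at their weekly video visits and testing is weekly during treatment, so both versions apply to the same occasions.

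**MMSE.** The two thresholds share no score, so no candidate can meet both. This bears on the remedy: neither list can be taken over whole without examining it.

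**The case against.** The best defence is that these are gaps in duplicate text, not opposing rules, and that other controls cover them. Much of this is right, and it rules out several stronger readings that a reader might infer.

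- **That Section 4.0 contradicts itself on seizures.** Exclusion 8 lists "lifetime history of seizures and/or epilepsy per the judgement of the medical clinician" among reasons for missing the scan, and says that people who fail only the MRI criteria "will still be eligible to reenroll in and complete the medication/treatment phase". But this keeps only those who already meet the criteria for the medication component. Someone excluded under exclusion 3 does not, so the repeat is redundant and readmits nobody.
- **That everyone with a seizure history is barred.** The exclusion rests on the medical clinician's judgement.
- **That the omission exposes people to a known risk of the study drug.** Section 14.0 does say: "These risks include seizures, mental disturbances, nausea, vomiting, irregular heartbeat" and others. It ties these to intravenous oxytocin and says they were not noted with intranasal use, which is this trial's route. The documents do not support the stronger inference.
- **That staff would scan an ineligible person.** Section 9.0 requires a metal questionnaire and a handheld detector. Section 14.0 requires a metal history for each participant, review by trained staff, documentation where a safety question arises, and a ferromagnetic wand. The MRI technician may exclude on other grounds, and scanning is optional. Such a scan is unlikely.
- **That the pregnancy statements cannot all be met.** None of the three shorter ones says that a verbal report alone is enough, and following the later Telehealth paragraph satisfies all four. Dosing is also observed on screen.

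The history and physical, which includes a neurological examination, is a further safeguard at entry.

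What remains is that none of these controls says which written rule applies. A person working only from Section 12.0, or only from a shorter pregnancy statement, would comply with the text in front of them and still apply a narrower rule than the protocol states elsewhere.

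**Conclusion.** The point stands as an internal inconsistency that bears on participant safety, not as a flaw in the design. Two trial-level exclusions in Section 4.0 are missing from the Section 12.0 list, the MRI metal rule has two scopes, and the telehealth pregnancy check is described three times as verbal and once as verbal plus photograph. The practical size cannot be estimated: the documents give no expected number of people with a seizure history or with metal below the waist, or of women attending by telehealth. The conclusion rests on reading both lists as current and operative, since nothing marks Section 12.0 as a summary of the criteria or gives either list precedence. No sample size, power, alpha or treatment-effect estimate changes. The amendment should be made because it is cheap and removes an ambiguity in who is enrolled, scanned and dosed.

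**What to change.** Reconcile the two eligibility lists item by item, then either keep one agreed list and cross-refer to it, or keep two identical ones. The reconciliation should cover the seizure and medical-condition exclusions, the items found only in Section 12.0, and the opposed MMSE thresholds. Simply deferring to Section 4.0 would not be sound: it would leave that section's MMSE threshold as the only one without anyone having examined it, and it would pre-empt the medical team's choice.

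State one MRI metal rule in both places. State one telehealth pregnancy-confirmation rule in General Procedures, both Telehealth statements and Study Safety, and say whether it applies before each dose. The medical team decides which version stands in every case; this review proposes none.

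The cost is a protocol wording amendment, with the screening form and telehealth visit checklist brought into line. No analysis or sample-size work is needed.
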